4.3. Treatment Assignment

Patients will be randomized (assigned to a treatment) by the site using interactive randomization technology (IRT).

Only the designated unblinded study personnel will have access to the randomization schedule until the study is completed and approval to unblind the treatment arm assignments has been made. Complete details regarding handling, storage, and security of the randomization schedule will be documented.

At the sparse PK sites, patients will be randomized to 1 of 4 treatment arms in a ratio of 5:5:5:4 (SPR720 low dose, SPR720 high dose, placebo, and SOC). The SPR720 and placebo arms will be double blinded, and the SOC arm will be open label. At intense PK sites a total of at least 18 patients will be randomized to Treatment Arms 1, 2, and 3 in a ratio of 1:1:1.

The IRT will stratify randomization by diagnosis at enrollment as either 1) nodular-bronchiectatic or 2) fibro-cavitary NTM-PD.

Patients will be identified by a unique 10-digit patient identifier (e.g., 201-YYY-ZZZZ) in which the first 3 digits indicate the study identifier (e.g., 201), the second 3 digits indicate the site number, and the final 4 digits indicate the number assigned at randomization. For example, the first patient randomized at site 001 will be identified by the number [contact]. Spero Therapeutics, Inc. will assign site numbers. As a double-blind study, the Investigators, the site staff, the Sponsor, and clinical monitors will not be aware of the treatment assigned to the

individual study patients except for Treatment Arm 4 (SOC), which is open label. Specific, documented staff at the sponsor and contract research organization (CRO) will be unblinded to treatment assignments.

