3. INVESTIGATIONAL PLAN

3.1. Overall Study Design and Plan

This is a Phase 2a, multicenter, randomized, partially blinded, placebo- and comparator-controlled study to evaluate the safety, tolerability, PK, and efficacy of 2 dose levels of SPR720 compared with placebo or SOC for the treatment of patients with NTM-PD due to MAC. The SPR720 and placebo arms will be double blinded, and the SOC arm will be open label.

Approximately 90 male and female patients 18 years of age and older with a diagnosis of NTM-PD due to MAC will be enrolled and treated for 28 days. Treatment-naïve patients must be ready to initiate treatment within the next 3 months. Patients who have received prior treatment may be eligible if they have culture evidence of persistent, recurrent, or relapsed disease; have been off therapy for at least 6 months; and are likely to reinitiate or resume treatment.

For the sparse PK sites, enrolled patients will be randomly assigned 5:5:5:4 (Arm 1: Arm 2: Arm 3: Arm 4) into one of the following treatment arms until 72 patients are enrolled (19 to 20 patients each for Treatment Arms 1, 2, and 3 and 15 to 16 patients for Arm 4). For the intense PK sites, enrolled patients will be randomly assigned 1:1:1 (Arm 1: Arm 2: Arm 3) into one of the following treatment arms (6 patients each for Treatment Arms 1, 2, and 3):

- **Treatment Arm 1: SPR720 Low Dose:** Double-blinded SPR720 investigational product (IP) 500 mg once daily for 28 days.
- **Treatment Arm 2: SPR720 High Dose:** Double-blinded SPR720 IP 1000 mg once daily for 28 days.
- **Treatment Arm 3: Placebo:** Double-blinded placebo once daily for 28 days.
- **Treatment Arm 4: SOC:** At Investigator's discretion. Recommended as follows: 2-drug or 3-drug SOC, including clarithromycin 500 to 1000 mg PLUS ethambutol hydrochloride (HCl) approximately 15 mg/kg or azithromycin 250 to 500 mg once daily PLUS ethambutol HCl approximately 15 mg/kg once daily for 28 days. Optional rifampin 600 mg or rifabutin 300 mg once daily for up to 28 days may be added to the SOC regimen.

Inform the medical monitor of alternative SOC regimens and discuss concerns or questions.

Randomization will be stratified by diagnosis at enrollment as either 1) nodular-bronchiectatic or 2) fibro-cavitary NTM-PD.

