3.3. Selection of Study Population

Approximately 90 male and female patients, 18 years of age and older, with a diagnosis of NTM-PD due to MAC will be enrolled in the study.

Specific entry criteria are detailed in [Section 3.3.1](#) and [Section 3.3.2](#).

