8. STATISTICAL CONSIDERATIONS

The statistical analysis will be undertaken by Synteract in collaboration with Spero.

A detailed statistical analysis plan (SAP) will be finalized and signed before database lock and before analysis of the study being carried out. Any deviations from the analyses described below will be included in the clinical study report.

Continuous variables will be summarized with means, standard deviations, medians, minimums, and maximums. Other summaries (e.g., quartiles, confidence intervals) may be used as appropriate.

Categorical variables will be summarized by frequency and by percentage of patients in corresponding categories.

All summary tables will be presented by treatment arm. Disposition, demographic, and baseline summaries will also include a total summary column. All data reported for a patient during the study and all derived data will be presented in data listings.

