8.1.9. Safety Analyses

Safety data will be summarized for the Safety Population. All safety presentations will be descriptive, and all summaries will be displayed by treatment arm.

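### SOC can be assigned only at sparse-PK sites, so in safety tables pooled by arm about 24% of each blinded arm and none of SOC come from intensive-PK sites, and reading an arm against SOC is not fully randomized

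*Combined protocol and SAP*

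**What the plan says.** Section 4.3 gives the two allocation schemes: "At the sparse PK sites, patients will be randomized to 1 of 4 treatment arms in a ratio of 5:5:5:4", and, separately, "At intense PK sites a total of at least 18 patients will be randomized to Treatment Arms 1, 2, and 3", at 1:1:1. The same section stratifies by diagnosis (nodular-bronchiectatic or fibro-cavitary); no other stratification factor is listed.

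Section 3.1 gives the counts. Sparse-PK sites enrol "until 72 patients are enrolled (19 to 20 patients each for Treatment Arms 1, 2, and 3 and 15 to 16 patients for Arm 4"). Intensive-PK sites contribute "6 patients each for Treatment Arms 1, 2, and 3". Section 3.3 puts the total at about 90. Sections 3.1, 4.3 and 5.3 also describe the intensive-PK number as a minimum of 18.

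On presentation, section 8 says: "All summary tables will be presented by treatment arm". Section 8.1.9 says: "All safety presentations will be descriptive, and all summaries will be displayed by treatment arm". Nothing visible restricts, splits or adjusts a summary by site type. The title and section 3.1 describe the study as comparing SPR720 with placebo or SOC, while section 8.1.4 plans no formal hypothesis.

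**The concern.** A randomized comparison needs every patient in it to have had a chance of either treatment. At intensive-PK sites the chance of SOC is zero. A by-arm safety table that includes all sites therefore sets SOC patients, all from sparse-PK sites, beside blinded arms drawn partly from a different group of sites. Any outcome difference between site types then becomes part of the apparent difference from SOC.

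The documents give two reasons why site types might differ.

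- **Observation.** Under Table 2 (footnotes l and m), intensive-PK patients are sampled out to 24 h after the dose on Days 1 and 28. Sparse-PK patients may leave after a sample taken at discharge or at least 3 h after the dose. Adverse events are elicited by an open question (section 6.3), so more contact may mean more opportunity to report.
- **Selection.** Intensive-PK sites are chosen as qualifying sites (section 3.1). Entry also rests on the investigator's view that delaying standard therapy is acceptable (inclusion criterion 7, exclusion criterion 1). At sparse-PK sites 4 of 19 patients, or 21%, start SOC at once; at intensive-PK sites none do.

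At stake is how far anyone may say that SPR720, or placebo, looks safer or less safe than SOC.

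**Working it through.** **Inputs.** Section 3.1: 72 sparse-PK patients, and 6 intensive-PK patients in each of Arms 1 to 3. Section 4.3: ratios 5:5:5:4 and 1:1:1. Section 3.3: about 90 in total.

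**1. Reproduce the plan's counts.**

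- Each blinded arm at sparse-PK sites: 72 × 5/19 = 18.95.
- SOC at sparse-PK sites: 72 × 4/19 = 15.16.
- Total: 3 × (18.95 + 6) + 15.16 = 90.

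These agree with the stated ranges and total.

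**2. Share of each arm from intensive-PK sites.** Share = n(intensive) / [n(sparse) + n(intensive)].

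| Sparse-PK per blinded arm | Intensive-PK per blinded arm | Share of blinded arm | Share of SOC |
|---|---|---|---|
| 18.95 | 6 | 24.05% | 0% |
| 19 | 6 | 6/25 = 24.0% | 0% |
| 20 | 6 | 6/26 = 23.1% | 0% |
| 19 | 7 | 7/26 = 26.9% | 0% |
| 19 | 8 | 8/27 = 29.6% | 0% |

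The last two rows apply if more than the minimum of 18 intensive-PK patients enrol.

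**3. Composition bias.** Let m be the expected SOC outcome at sparse-PK sites, θ the treatment difference (taken as equal at both site types), and δ the intensive-minus-sparse difference in outcome. A pooled blinded arm has expectation m + θ + 0.24δ and SOC has m, so the pooled difference is θ + 0.24δ. The bias is 0.24δ.

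The documents give no value for δ. With assumed values:

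- 10 points: 0.24 × 10 = 2.4 points.
- 20 points: 0.24 × 20 = 4.8 points. For example, with rates of 20% and 40% in the two site types, the pooled arm is 0.76 × 20 + 0.24 × 40 = 24.8%.
- 30 points: 0.24 × 30 = 7.2 points.

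**4. Precision cost of restricting to sparse-PK sites.** The contrast becomes 19 versus 15 instead of 25 versus 15. With equal variance, the standard-error ratio is √(1/19 + 1/15) / √(1/25 + 1/15) = √(0.1193/0.1067) = 1.058, about 6% larger.

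**5. When restriction improves accuracy.** Assume a 40% incidence, so the variance per patient is 0.4 × 0.6 = 0.24.

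- Pooled standard error: √(0.24 × 0.1067) = 16.0 points.
- Restricted standard error: √(0.24 × 0.1193) = 16.9 points.
- Mean squared error favours restriction when the bias exceeds √(0.02863 − 0.02560) = 5.5 points, that is, when δ exceeds 5.5/0.24, about 23 points.

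**6. Comparisons not touched.** Arms 1 to 3 are allocated equally to one another at both site types, so the site mix cancels among them. SOC patients give no PK samples (section 3.1), so the primary PK endpoint involves no SOC comparison.

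**The case against.** The strongest reply is that no contrast with SOC is visible as a planned estimate. The primary objective is PK, section 8.1.4 words efficacy as SPR720 against placebo, and safety is descriptive. What remains is a reader looking across adjacent columns. That stands, and it limits the priority. It does not remove the point: comparison with SOC is in the title and the design statement, and with no formal test planned, reading across columns is how the comparison will be made.

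Second, the bias is hypothetical and small beside the noise. That also stands. By step 5, two of the three assumed site-type differences fall below the level at which restriction lowers mean squared error, so replacing every display that shows SOC with a restricted one would be excessive. The case for a restricted display is that it is a randomized comparison, not that it is sure to be more accurate.

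Third, restriction leaves other differences in place. Even at sparse-PK sites, SOC is open label, has no PK draws or Day 56 visit, and may have vital signs and ECGs at any time (section 3.1, Table 2 footnotes). This is correct. Site types also share visit days, the adverse event question and a central laboratory, so the only documented difference in observation is the denser sampling on Days 1 and 28. Differences in case mix are conjecture.

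A reader might infer that all analyses, efficacy included, pool over site type. The documents do not support that. The efficacy analyses and part of the analysis-population text are redacted, section 8 defers detail to a SAP to be finalized before database lock, and a by-arm layout does not by itself exclude a split by site type.

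**Conclusion.** The design fact is certain: SOC is assigned only at sparse-PK sites, and the visible safety and general summaries are by arm with no site-type split. On planned counts, 23% to 24% of each blinded arm and 0% of SOC come from intensive-PK sites, with a larger share if intensive-PK enrolment exceeds 18. A pooled arm set beside SOC is therefore only partly randomized.

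The multiplier of about 0.24 follows from the design, assuming the treatment difference is the same at both site types. The size and direction of the bias are unknown, because they depend on a site-type difference that the documents do not give. It would be wrong to conclude that SPR720-versus-SOC results are shown to be biased by a stated amount, or that the randomized comparison with placebo is weakened. This is a modest reporting improvement, confined to the visible safety and general summaries.

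**What to change.** Keep the all-site tables by treatment arm. In the SAP, before database lock, prespecify for the main safety tables (treatment-emergent adverse events, serious adverse events, key laboratory shifts) a supportive display limited to sparse-PK-site patients, about 19/19/19/15, who were randomized among all four arms. Make that display the basis for any statement about SPR720 or placebo against SOC. Continue to use all sites for comparisons among Arms 1 to 3. Footnote the pooled tables to say that patients at intensive-PK sites could not be assigned SOC.

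No new data are needed, since the site number is part of the patient identifier (section 4.3). The cost is a few extra tables and the precision loss in step 4. The report should still state the open-label SOC arm and its different in-clinic observation as limitations.

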4.4. Drug Packaging and Blinding

The IP will be labeled in such a way that the blind is maintained.

The Investigator can receive a patient's assigned treatment through the IRT system if knowledge of the IP is necessary for emergency treatment. If possible, the Medical Monitor should be consulted before breaking the code. In any case, the Investigator must record the date, time, and reason for breaking the code. The Investigator, once unblinded, should not share the treatment assignment with site, Sponsor, or CRO personnel. The Sponsor must be notified as soon as possible if the blind must be broken.

A copy of the randomization code will be maintained securely by the CRO. Designated unblinded personnel will be able to access the randomization code if needed.

Additional information can be found in the Pharmacy Manual.

4.5. Drug Inventory and Accountability

The Investigator must keep an accurate accounting of the number of IP units delivered to the site, dispensed to patients, returned to the Investigator by the patient, and returned to the Sponsor or destroyed locally or other disposition during and at the completion of the study.

The IP is to be used in accordance with the protocol by patients who are under the direct supervision of the Investigator. The IP will be sent home with patients for drug administration between clinic visits. Investigators should maintain records that document adequately that the patients were provided the doses specified by the protocol and reconcile all IP received at the site before final disposition. Procedures for the return or destruction of both the used and unused IP will be described in the Pharmacy Manual.

Investigators are required to report IP quality complaints to the Sponsor as described in the Pharmacy Manual.

Full details of IP receipt and storage will be documented in the Pharmacy Manual.

4.6. Treatment Compliance

All patients will be asked to document in a provided diary the date and time of each IP or SOC dose taken at home, along with other requested information related to IP administration.

Patients will be required to bring the IP wallet the subsequent clinic visit including any remaining capsules that have not been taken. At each visit, the patient's remaining capsules and the diary will be retrieved by the Investigator and compliance assessed.

Investigational product wallets must be returned at each visit, as compliance will be assessed by capsule counts. Investigational product noncompliance for a patient is defined as taking less than 80% or more than 120% of IP during the treatment period (Day 1 through EOT). Discontinuation for noncompliance is at the Investigator's discretion and should be documented accordingly.

4.7. Concomitant Illnesses and Treatments

4.7.1. Concomitant Illnesses

Medical history, including significant illnesses, should be documented in the electronic case report form (eCRF) according to completion guidelines.

Additional illnesses present at the time informed consent is given are to be regarded as concomitant illnesses. Illnesses first occurring or detected after first dose and/or worsening of a concomitant illness during the study are to be documented as AEs in the eCRF.

4.7.2. Concomitant Treatments

Concomitant medications and treatments, defined as treatments taken after the first dose of IP and SOC, should be recorded in the eCRF according to completion guidelines. Medications and treatments taken before the first dose of IP or SOC will not be recorded in the eCRF.

Patients should not have used any systemic (po or IV) or inhaled antibiotic with activity versus MAC between screening and randomization. Drugs or supplements that are strong CYP3A4 enzyme inducers or inhibitors (see [Appendix 1](#)) within 4 weeks of randomization and during the study are prohibited. Hepatic transporters, OATP1B1 or OATP1B3, (see [Appendix 2](#)) within 1 week of randomization and during the study are prohibited.

Any medication or therapy that is taken by or administered to the patient during the study will be recorded (see completion guidelines for eCRF).

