4. INVESTIGATIONAL PRODUCT

4.1. Identity of the Investigational Product

Investigational product refers to both SPR720 and placebo in this Investigational Product section.

SPR720 will be administered po as 250 mg capsules containing SPR720 as the active substance with no additional excipients. The capsules are white, opaque, size 0, hard gelatin capsules containing a white powder. Placebo doses will also be administered po as white, opaque, size 0, hard gelatin capsules containing an approximately equivalent weight of microcrystalline cellulose (white powder).

SPR720 drug product and placebo are manufactured by Patheon UK Limited (Abingdon, Oxfordshire, UK) under Good Manufacturing Practice conditions and packaged, labeled, and distributed by Almac Clinical Services.

SPR720 and placebo are packaged in blister cards of 28 capsules each and then packaged into wallets that will be given to the patient.

Additional information is provided in the investigator's brochure (IB) and in the Pharmacy Manual.

Standard of care (SOC) will be obtained by the study sites or by prescription. Refer to the Product Package Inserts for detailed information regarding SOC treatments.

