4.2. Dosage Schedule

Dosing for each treatment arm is displayed in [Table 1](#). Study drug will be taken po once daily for 28 days (Days 1 through 28). Dosing for Treatment Arms 1, 2, and 3 will take place at the clinic on study visit days. The clinic and patient should try to schedule clinic visits as early as possible in the morning to accommodate pre-dose study activities and dosing, preferably before a meal. Patients in Treatment Arms 1, 2, and 3 should make every effort to take the IP at the same time in the morning approximately an hour before a morning meal on an empty stomach. There are no liquid restrictions. Patients will receive a supply of IP and instructions for documenting at-home dosing. If a patient experiences IP tolerability issues while at home, the site should instruct the patient to call the Investigator. The Investigator may instruct the patient to take their dose with a snack or meal, if clinically indicated, to alleviate tolerability concerns. Dosing for Treatment Arm 4 (SOC) should occur per specific prescribing information instructions.

Table 1: Study Treatments

Treatment Arm 1	Double-blinded SPR720 IP 500 mg (2 capsules of 250 mg SPR720 and 2 capsules of placebo) po once daily
Treatment Arm 2	Double-blinded SPR720 IP 1000 mg (4 capsules of 250 mg SPR720) po once daily
Treatment Arm 3	Double-blinded placebo (4 capsules of placebo) po once daily
Treatment Arm 4	
Standard of Care regimen is at the Investigator's discretion; recommended 2-drug or 3-drug SOC, consisting of either:
 
 • Clarithromycin 500-1000 mg, plus ethambutol HCl 15 mg/kg po once daily or • Azithromycin 250-500 mg, plus ethambutol HCl 15 mg/kg po once daily 
Optional rifampin 600 mg or rifabutin 300 mg po once daily may be added to the SOC regimen for up to 28 days.
 
Inform the medical monitor of alternative SOC regimens and discuss concerns or questions.

Abbreviations: HCl=hydrochloride; IP=investigational product; po=orally; SOC=standard of care.

Note: Patients will be treated for 28 days.

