APPENDIX 1. PROHIBITED INHIBITORS AND INDUCERS OF CYP3A

The following inhibitors and inducers of CYP3A are prohibited within 4 weeks before randomization and during the study:

CYP3A Strong Inhibitors	CYP3A Strong Inducers
Boceprevir	Carbamazepine
Cobicistat	Enzalutamide
Conivaptan	Mitotane
Danoprevir and ritonavir	Phenytoin
Elvitegravir and ritonavir	Rifampin
Grapefruit juice	St. John's wort
Indinavir and ritonavir	
Itraconazole	
Ketoconazole	
Lopinavir and ritonavir	
Paritaprevir and ritonavir and (ombitasvir and/or dasabuvir)	
Posaconazole	
Ritonavir	
Saquinavir and ritonavir	
Telaprevir	
Tipranavir and ritonavir	
Troleandomycin	
Voriconazole	
Clarithromycin	
Diltiazem	
Idelalisib	
Nefazodone	
Nelfinavir	

Abbreviation: CYP=cytochrome P450

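### Section 4.7.2 and Appendix 1 prohibit clarithromycin and rifampin during the study in no named arm, yet the Arm 4 regimen recommends the first and allows the second

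*Combined protocol and SAP*

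**What the plan says.** On CYP3A, section 4.7.2 states that strong CYP3A4 inducers or inhibitors "within 4 weeks of randomization and during the study are prohibited". Appendix 1 says: "The following inhibitors and inducers of CYP3A are prohibited within 4 weeks before randomization and during the study". Its list puts clarithromycin under strong inhibitors and rifampin under strong inducers.

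On Arm 4, section 3.1 recommends a "2-drug or 3-drug SOC, including clarithromycin 500 to 1000 mg PLUS ethambutol hydrochloride (HCl) approximately 15 mg/kg", or azithromycin plus ethambutol. Table 1 in section 4.2 gives the same two options and adds: "Optional rifampin 600 mg or rifabutin 300 mg po once daily may be added to the SOC regimen for up to 28 days".

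On what counts as concomitant, section 4.7.2 describes concomitant medications as "defined as treatments taken after the first dose of IP and SOC". Section 4.1 states: "Investigational product refers to both SPR720 and placebo in this Investigational Product section".

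On MAC-active antibiotics, the same paragraph of 4.7.2 that holds the CYP3A4 rule says: "Patients should not have used any systemic (po or IV) or inhaled antibiotic with activity versus MAC between screening and randomization". The CYP3A4 and OATP restrictions that follow it both continue through the study. Section 4.7.2 closes with a recording duty: "Any medication or therapy that is taken by or administered to the patient during the study will be recorded".

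**The concern.** The main point is a conflict between two operative parts of the protocol. One names drugs that Arm 4 patients may be given as their assigned regimen. The other prohibits those same drugs for the whole study and does not say for whom. Two sites could reasonably treat clarithromycin in Arm 4 differently: one prescribes it as recommended, and the other avoids it or logs a deviation. Section 8.1.6 leaves deviations to case-by-case assessment, so the text does not settle the matter later either.

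The secondary point concerns Arms 1 to 3. Section 8.1.4 states an aim of evaluating the efficacy of SPR720 against placebo, and sputum is collected in these arms to Day 56. A MAC-active drug started after randomization could affect later sputum results. The paragraph that would be expected to govern such drugs gives a period that ends at randomization.

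**Working it through.** This is mainly a comparison of passages. Arithmetic is needed only for scope.

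**Step 1: does the prohibition reach Arm 4 as written?**
- Period: section 3.2 gives Arm 4 a screening period and 28 treatment days, and section 3.1 ends its participation at the end-of-treatment visit. All Arm 4 dosing therefore falls during the study.
- Arms: neither 4.7.2 nor Appendix 1 names one.
- Exemption: neither mentions assigned SOC.
- Result: clarithromycin or rifampin given under Table 1 meets the literal terms of the prohibition.

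**Step 2: can Arm 4 comply with both passages?**
- Azithromycin, ethambutol and rifabutin appear in neither Appendix 1 nor Appendix 2.
- Azithromycin plus ethambutol, with or without rifabutin, therefore satisfies 4.7.2 and Table 1 together.
- Result: the conflict covers one of the two macrolide options and one of the two optional rifamycins, not the whole arm.

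**Step 3: which visible rules limit MAC-active drugs in Arms 1 to 3 after randomization?**
- Section 1.1.2 names clarithromycin, azithromycin, rifampin, rifabutin, ethambutol, streptomycin and amikacin for MAC pulmonary disease.
- Clarithromycin and rifampin are barred by the CYP3A rule.
- The other five are in neither appendix.
- Section 6.10 makes use of a treatment other than the assigned one reportable as a medication error. This arguably reaches the Arm 4 drugs in Table 1 (azithromycin, ethambutol, rifabutin), but it is a reporting duty, not a restriction.
- Inclusion 7 and exclusion 1 imply that standard therapy is deferred while the patient takes part. They are entry judgements.
- Result: no visible passage restricts the other five drugs after randomization.

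**Step 4: scope.** Inputs are from section 3.1: 72 patients at sparse PK sites allocated 5:5:5:4 (sum 19), plus 6 in each of Arms 1 to 3 at intense PK sites.
- Each of Arms 1 to 3, sparse sites: 72 × 5/19 = 18.9 (protocol: 19 to 20).
- Arm 4: 72 × 4/19 = 15.2 (protocol: 15 to 16), which is 15/90 = 16.7% to 16/90 = 17.8% of the planned total.
- Arms 1 to 3 together: 72 × 15/19 + 18 = 56.8 + 18 = 74.8, about 75.
- Check: 74.8 + 15.2 = 90, the stated total.
- Post-baseline sputum in Arms 1 to 3: Days 6/7, 13/14, 20/21, 27/28 and 55/56, so five paired time points. The last comes 56 − 28 = 28 days after treatment ends.

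These figures describe arm size and schedule. They do not measure exposure to such drugs, and every post-baseline sample follows randomization by definition.

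**The case against.** On the main point, the best reply is that assigned SOC is study treatment and so lies outside a section on concomitant treatments. The text supports this: 4.7.2 sets SOC beside IP in its definition, Table 1 is titled as a table of study treatments, and the diary in section 4.6 covers both IP and SOC doses. A regimen named for one arm would also normally prevail over a general rule, and Arm 4 has no PK sampling, so the rule may never have been meant for it. The reading is plausible, but no passage states it. Section 4.1 limits IP in section 4 to SPR720 and placebo, although that alone does not make assigned SOC a concomitant drug. Appendix 1 is not confined to concomitant use.

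On the secondary point, much of the opposing case stands. The entry criteria describe a delay that must run past randomization, section 6.10 captures some use, and the two drugs listed in Appendix 1 are already barred. A reader might infer that exclusion 7 is also defective because it ends at randomization. It is not: an entry criterion naturally ends there, and it conflicts with nothing. A reader might also infer that the plan has no way of handling sputum data after such use. The documents do not support that, because the efficacy sections are redacted and section 8 promises a detailed SAP before database lock.

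**Conclusion.** The conflict over clarithromycin and rifampin stands as written. It concerns two named drugs in an arm of 15 to 16 patients, and its consequence is inconsistent prescribing or deviation logging in that arm. It does not touch the PK endpoint. A reader might go further and conclude that Arm 4 cannot receive its recommended treatment; Step 2 shows that this is wrong.

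The secondary point stands in a limited form. The period stated for the MAC-active antibiotic restriction stops at randomization, and only partial visible limits apply in Arms 1 to 3 after that. The consequence is modest: the primary endpoint is PK, section 8.1.4 plans no formal hypothesis, and the documents say nothing about how often such drugs would be started. No bias is claimed or sized.

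Both conclusions rest on the visible text. Redacted efficacy text or the later SAP could settle analysis handling for the secondary point. Analysis text would not by itself remove the conflict between 4.7.2 with Appendix 1 and 3.1 with Table 1.

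**What to change.** 1. Reconcile section 4.7.2 and Appendix 1 with section 3.1 and Table 1: state which arms and what period the CYP3A prohibition covers, and whether assigned SOC counts as study treatment. Classify deviations to match. The clinical rule is for the sponsor to choose.
2. In the same paragraph of 4.7.2, state the arms and period that the MAC-active antibiotic restriction covers. Exclusion 7 needs no change.
3. From the concomitant medication data, identify MAC-active antibiotics started after randomization in Arms 1 to 3. Recording in the eCRF starts at the first dose, so the flag covers use from then on.
4. Only if the redacted efficacy text or the SAP does not already do so, add a sentence on how sputum data after such use are treated in the SPR720 and placebo summaries.

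The cost is protocol wording, one derived flag and possibly one SAP sentence. No new data are needed: section 4.7.2 already requires on-study medication to be recorded, and section 8.1.9.3 already codes and summarizes it by ATC class and preferred name.
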